11. ANALYSIS OF EXPLORATORY OUTCOME MEASURES

The exploratory objective stated in the protocol is to explore effects of inhaled sargramostim on biological responses to COVID-19.

11.1. Exploratory Efficacy Outcome Measures

11.1.1. Proportion of patients requiring supplemental oxygen up to Day 28

Numbers and proportions of patients requiring any supplemental oxygen up to Day 28 will be summarized by treatment arm along with a summary by modality of oxygen supplementation support required for the FAS. For modality of oxygen supplementation required, each patient will be counted once per type required even if they required support in more than one instance. Number of days on oxygen support will also be summarized, for the FAS, with the number of days calculated using the difference between the start and end date-times recorded on the eCRF. Patient level listings of supplemental oxygen use will be provided for the FAS including patient ID, treatment arm, randomization strata, age, race, and sex. Any partial or missing dates will be reported as recorded in the study data on patient listings.

11.1.2. Presence or absence of COVID-19 symptoms at Day 60

The presence or absence of COVID-19 symptoms at Day 60 will be assessed for the FAS. This questionnaire data will be tabulated by question (symptom), in terms of the number and proportion of patients who have specific symptoms reported in the 7 days prior. A summary of the number of patients who completed or missed the Day 60 visit will also be provided. This symptom assessment is expected to be completed for patients at study discontinuation, if earlier than Day 60. There will be no imputation of missing data for this analysis. Patient level listings of presence or absence of COVID-19 symptoms at Day 60 will be provided for the FAS including patient ID, treatment arm, randomization strata, age, race and sex. Any partial or missing dates will be reported as recorded in the study data on patient listings. The data may also be presented graphically such as using a stacked bar chart, etc. by question (symptom) and by treatment arm.

11.2. Exploratory Safety Outcome Measures: Levels of ferritin, c-reactive protein (CRP), d-Dimer up to Day 28

Levels of ferritin, CRP, and d-Dimer on Days 1, 5, 14, and 28 will be summarized by treatment arm along with change from baseline for the Safety Population. The number of patients with missing values will be tabulated. Patient level listings of levels of ferritin, CRP, and d-Dimer up to Day 28, will be provided for the Safety Population including patient ID, treatment arm, randomization strata, age, race, and sex. Any partial or missing dates will be reported as recorded in the study data on patient listings.

11.3. Exploratory Outcome Measures for the Biomarker Cohort Only

Four additional measures will be assessed only for the Biomarker Analysis Population. These measures are: the effect of sargramostim on SARS-CoV-2 viral load in samples collected from nasopharyngeal swabs up to Day 14; proportion of patients with generation of SARS-CoV-2 antibody up to Day 28; proportion of patients with markers of cellular immunity, via immunophenotyping, up to Day 14; and immunogenicity to sargramostim up to Day 28. The

planned analysis of biomarker data for the biomarker cohort will be detailed separately in a Biomarker SAP Addendum, and finalized prior to any unblinding of the study team.

12. EXPLORATORY ANALYSES

12.1. Subgroup Analysis and Adjustment for Covariates

All subgroup analyses and covariate adjustments will be treated as exploratory since the study was not powered for such analyses. These analyses will be conducted using the FAS, unless otherwise specified. The following baseline characteristics will be considered for subgroup analyses and covariate adjustment in statistical models. Additional baseline factors may be considered for these analyses and a decision on which factors to include will be made while the study team remains blinded.

- Age group (18-59, \geq 60 years). For regulatory purposes, an additional analysis may be performed using age groups defined as 18-64, and \geq 65 years. If there are enough patients \geq 75 years or \geq 85 years, these categories may be included.
- Number of pre-existing medical conditions which put patients at higher risk of progression to severe COVID-19 (0-1, 2 or more), based on Inclusion Criterion 3b. Note: age will be considered separately as denoted above. If there are enough patients for any specific pre-existing condition in Inclusion Criterion 3b, a subgroup analysis may be performed for this.
- Duration of any COVID-19 symptoms (0-2, 3-5 days)
- Baseline NIAID ordinal score (1, 2)
- Gender (male, female)
- Race (White, Black or African American, Asian, all others)
- Ethnicity (Hispanic or Latino, Not Hispanic or Latino)
- Body mass index ($<18.5 \text{ kg/m}^2$, $18.5 \text{ to } <25 \text{ kg/m}^2$, $\geq 25 \text{ to } <30 \text{ kg/m}^2$, $\geq 30 \text{ kg/m}^2$)
- Baseline SARS-CoV-2 variant (groupings to be determined based on prevalence)
- Use of approved/authorized COVID-19 therapies prior to randomization (if there are sufficient number of patients)

In addition to the above baseline factors, the following 2 randomization stratification factors will be used for subgroup analyses and included in all covariate adjustment models if there are sufficient patients in each of the strata.

- Region (US, outside US)
- Completion of a COVID-19 vaccination regimen or participation in a COVID-19 vaccine clinical trial (yes, no).

Prior to performing analyses, blinded review of baseline characteristics and randomization stratification factors will be performed to evaluate whether there are enough patients in each category. If there are insufficient numbers of patients in each category, some categories may be combined. Conversely, if there are more patients than expected in each category, additional categories may be considered. Additionally, collinearity between factors will be assessed prior to beginning any covariate adjustment. Any missing baseline factors will be accounted for using a missingness indicator (Groenwold et al. 2012).

Subgroup analyses will be conducted for the primary endpoint, and if warranted, for other efficacy endpoints. If there is an indication of differential treatment effect for the primary endpoint, then the subgroup analyses may be performed on secondary endpoints. Subgroup by treatment interactions will be included to assess differential treatment effects. If a meaningful differential treatment effect is observed across efficacy endpoints, then safety analysis may be performed for the subgroup(s) of interest. Furthermore, as the COVID-19 science continues to evolve, additional subgroups of interest may be identified.

As with the subgroup analyses, covariate adjustment will be performed for the primary endpoint, and if warranted, for other efficacy endpoints. A logistic or Cox proportional hazards regression model (based on type of endpoint) as described in [Section 9.1](#) or [Section 9.2](#) and will occur in 2 stages:

1. First, each baseline factor will be assessed in a model including treatment arm and selected randomization stratification factors to determine if each baseline factor has a potential impact on the outcome of interest. Factors will be assessed based on a univariate p-value < 0.1 .
2. Next, all baseline factors with a univariate p-value < 0.1 will be added into a multivariate model containing treatment and randomization stratification factors. A stepwise approach using a significance level of 0.05 to enter the model and a significance level of 0.1 to remain will be used to determine the final covariate-adjusted model for each outcome of interest.

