4. GENERAL ANALYTIC CONSIDERATIONS

4.1. Study Size and Power

A total of approximately 500 patients will be randomized using a 1:1 assignment ratio. The sample size is selected to achieve at least 80% power to detect a difference at the 0.05 level of significance (2-sided) in the proportion of patients who experience any emergency room visit or hospitalization, or death over 28 days.

This sample size is based on an assumed 3% event rate for the sargramostim arm and a 10% rate for the placebo arm (risk ratio of 0.30) in unvaccinated patients (similar to that observed for bamlanivimab BLAZE-1 study [Chen, 2021; Gottlieb, 2021; US FDA, 2021]). As discussed in protocol Section 4.6, the rate of any emergency room visits or hospitalization, or death over 28 days is expected to be very low, or near zero for vaccinated patients.

It is also assumed that the proportion of vaccinated patients will be approximately 20-25% of the study population, with enrollment of patients who have completed a COVID-19 vaccination regimen or participated in a COVID-19 vaccine clinical trial capped at approximately 100 patients; no events are expected to occur in these patients for either treatment arm. Therefore, the overall event rate (for unvaccinated and vaccinated patients combined) for the primary endpoint is expected to be 2.4% for sargramostim and 8.0% for placebo (risk ratio of 0.30) and maintains at least 80% power.

Note that completion of a COVID-19 vaccination regimen or participation in a COVID-19 vaccine clinical trial (yes, no) is one of the randomization stratification factors (protocol Section 6.2).

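### The exploratory adjusted analysis of the primary endpoint picks its covariates by p-value on about 26 events; a small set fixed in advance, with age continuous, is a cheap improvement

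*SAP*

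**What the plan says.** SAP Section 12.1 introduces ten baseline factors with one sentence: "The following baseline characteristics will be considered for subgroup analyses and covariate adjustment in statistical models". Age is split at 60 (with a possible further analysis split at 65, and older categories if numbers allow), the number of Inclusion Criterion 3b conditions is 0-1 or 2 and over, symptom duration is 0-2 or 3-5 days, and BMI has four classes. The list may be extended, and "a decision on which factors to include will be made while the study team remains blinded".

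Covariate adjustment is definite for the primary endpoint and conditional for other efficacy endpoints. It has two stages.

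- Stage 1 fits each factor in a model with treatment arm and selected stratification factors: "Factors will be assessed based on a univariate p-value < 0.1".
- Stage 2 takes the survivors into a stepwise procedure with entry at 0.05 and stay at 0.1, run for each outcome analysed.

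Region and vaccination status bypass the selection if their strata are large enough. The same section labels all covariate adjustment exploratory. The primary test in Section 9.1 is a Firth logistic regression with treatment only.

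Section 4.1 gives the size: "A total of approximately 500 patients will be randomized using a 1:1 assignment ratio", with "an assumed 3% event rate for the sargramostim arm and a 10% rate for the placebo arm" in unvaccinated patients. The overall rate "is expected to be 2.4% for sargramostim and 8.0% for placebo (risk ratio of 0.30) and maintains at least 80% power".

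**The concern.** Groups are needed for subgroup tables. In an adjustment model they discard information that has already been collected, most clearly for age. The selection then decides, on the trial's own outcome, whether a factor is used at all. With few events, a real risk factor can easily miss the thresholds, and a factor with no relation to outcome can pass by chance.

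Three things are at stake.

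- The primary model has treatment only, and the stratified sensitivity analysis in Section 9.1 is conditional and covers only the stratification factors. Section 12.1 is therefore the one specified treatment-effect model of the primary endpoint that could correct a chance imbalance in age or risk conditions, and it may contain neither.
- Both stages need treatment codes, so the final covariate set is unknown until they are used. The reported interval for the adjusted effect will not reflect the selection.
- Section 13 relaxes the screen from 0.05 to 0.1 so that useful factors are not lost early. Entry at 0.05 in stage 2 takes back much of that.

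**Working it through.** **Plan's own power.** Inputs from Section 4.1: 250 per arm, 8.0% v 2.4%, two-sided 0.05. Pooled rate = (0.080 + 0.024)/2 = 0.052.

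- z = [0.056 × √250 − 1.96 × √(2 × 0.052 × 0.948)] / √(0.080 × 0.920 + 0.024 × 0.976) = (0.885 − 0.615)/0.311 = 0.87
- Power = Φ(0.87) = 80.7%, which reproduces the stated figure of at least 80%.

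**Events.** 250 × 0.080 + 250 × 0.024 = 20 + 6 = 26. Section 4.1 also assumes that "the proportion of vaccinated patients will be approximately 20-25% of the study population". At 25% the count is 187.5 × (0.10 + 0.03) = 24.4.

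**Terms.** The ten candidates need about 14 parameters: race 3, BMI 3, and one each for the other eight (taking variant as two groups). Treatment and two strata make about 17, so 26/17 ≈ 1.5 events per term.

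**Closed-form check of one factor.** Assume a binary factor with 50% prevalence and OR 2, with overall rate 26/500 = 0.052. The two group rates are then about 3.55% and 6.85%.

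- SE of the log-OR = √[1/(250 × 0.0685 × 0.9315) + 1/(250 × 0.0355 × 0.9645)] = 0.424
- z = 0.693/0.424 = 1.64
- Chance of p < 0.1: Φ(1.64 − 1.645) ≈ 50%. Chance of p < 0.05: Φ(1.64 − 1.96) ≈ 37%.

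A true doubling of the odds therefore passes the screen about half the time and the entry threshold little more than a third of the time.

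**Simulation of the SAP steps, common OR.** Firth logistic regression with treatment and both strata, N = 500, 600 trials per row. Assumed: 50% prevalence for age 60 or over and for 2 or more conditions, the same OR for both, and eight unrelated factors.

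| OR | Age left out | Conditions left out | Both kept | At least one unrelated factor kept |
|---|---|---|---|---|
| 1.5 | 83% | 84% | 3% | 29% |
| 2 | 62% | 66% | 14% | 27% |
| 2.5 | 50% | 46% | 28% | 31% |
| 3 | 30% | 31% | 48% | 30% |

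At OR 2, age is kept in 38% of trials, in line with the closed form. For eight independent null tests at 0.05 the bound is 1 − 0.95^8 = 34%.

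**Simulation with moderate effects.** Assumed ORs are 1.5 per 10 years of age, 2.0 for 2 or more conditions and 1.5 for NIAID score 2, with 10% v 3% in 400 unvaccinated patients and no events in 100 vaccinated. Two separate runs, of 5,000 and 1,500 trials, gave:

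- age left out in 41% and 42%;
- condition count left out in 63% and 63%;
- baseline NIAID score left out in 85% and 87%;
- at least one unrelated factor kept in 25% and 23%.

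**Cost of grouping age.** In the 5,000-trial run, age passed the 0.1 screen in 69% of trials when cut at 60 and in 84% when continuous. As a cross-check, a median split of a normal covariate keeps 2/π ≈ 64% of the information. With OR 1.5 per SD and SE = 1/√(26 × 0.948) = 0.201, the chance of p < 0.05 is Φ(2.01 − 1.96) = 52% continuous and Φ(2.01 × √0.637 − 1.96) = 36% split.

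**Power for the adjusted treatment effect.** A fixed set of strata, continuous age, conditions and NIAID score gave 83.3% against 82.5% for the planned selection, and 86.0% against 84.4% with stronger effects. That set is incomplete. When prior authorized therapy was made strongly protective, it gave 83.6% against 83.9%. With prior therapy added, the fixed set had the higher estimate in all four settings run: 85.7 v 83.9, 84.7 v 83.2, 83.9 v 83.0 and 86.5 v 85.4 (%), with a paired standard error of about 0.5 points. The differences are 1.8, 1.5, 0.9 and 1.1 points.

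**Type I error.** The fixed model (without prior therapy) gave 5.0% and 4.6%, and the selection procedure did not inflate it.

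**The case against.** The strongest reply is that this analysis decides nothing. Section 12.1 labels it exploratory, Section 9.1 rests the conclusion on the unadjusted model, and Section 12.2 leaves room for other adjusted analyses. That stands, and it limits the point to the quality of a supporting estimate. A reader might infer that the primary result or its error rate is compromised; the SAP does not support that.

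A reader might also see a contradiction between the blinded decision on factors and a selection that needs treatment codes. There is none. The sentence on blinding concerns which factors become candidates, and the thresholds are set in advance. Blinding simply cannot extend to the result of the selection.

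Two other strong readings fail. Selection is not close to chance: under moderate effects age is kept in about 59% of trials, while seven unrelated factors together get one in about a quarter of the time. Nor does selection by outcome destroy comparability between endpoints: adjustment beyond the primary endpoint is conditional, and odds ratios and hazard ratios for different outcomes are not directly comparable even with identical covariates.

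Finally, a fixed set can miss a predictor that matters. Section 4.1.1 expects event rates near zero in patients given authorized therapies, so a set without prior therapy can do slightly worse than the planned selection. That objection stands, and the fix includes the variable for this reason.

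**Conclusion.** The point holds as a cheap improvement to an exploratory analysis. With about 26 events, the planned selection will often produce an adjusted model without age, without the condition count, or without both. Under moderate effects the omission rates are about 40% and 63%. Even at an OR of 3 for each, both are kept in fewer than half of trials. The interval from the selected model ignores the selection.

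The gain from fixing the set is mainly a known, stable and interpretable model. The power gain is small, roughly 1 to 2 points, and rests on including prior therapy.

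The event count and the selection rules follow from the SAP. The prognostic effects, covariate distributions and prevalences are assumptions, since the SAP gives none. The omission rates move with them, from 83% for age at OR 1.5 to 30% at OR 3.

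**What to change.** In Section 12.1, before unblinding, define the main exploratory adjusted model as a fixed set:

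- treatment;
- region and vaccination status, where strata suffice as already provided;
- age in years, continuous;
- number of Inclusion Criterion 3b conditions, stating whether it enters as 0-1 v 2 or more or as a count;
- baseline NIAID score;
- approved or authorized COVID-19 therapy before randomization, if blinded review finds enough users.

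This is seven terms at most, or 26/7 ≈ 3.7 events per term, with Firth estimation kept for binary endpoints. Use the same set for the other binary and time-to-event efficacy endpoints wherever adjustment is done. Keep the groupings for subgroup tables. The stepwise procedure can stay as a supplementary analysis.

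The cost is SAP wording; every variable is already on the SAP's list or underlies a grouping on it. The downsides are that age is assumed linear on the model scale and that the main adjusted model cannot adapt to an unexpected predictor.

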12.2. Other Exploratory Analyses

In addition to the previously specified exploratory analyses, additional exploratory analyses may be performed to evaluate the robustness and sensitivity of the study results, including but not limited to the analysis populations, subgroup analyses, treatment interactions, adjusted or stratified analyses, and/or alternative statistical methods.

For example, if there are meaningful differences in the results for the primary endpoint based on the mITT population compared to the analyses based on the FAS, then analyses of the secondary endpoints may be performed for the mITT population.

13. CHANGE FROM ANALYSIS SPECIFIED IN THE CORRESPONDING PROTOCOL VERSION

Section 12.1 includes a small change from the protocol in the covariate adjustment process. Instead of assessing baseline factors at a significance level of 0.05, factors will be assessed for inclusion into the stage 2 modeling based on a significance level of 0.1. This change was made due to an acknowledgement that some factors that may not be significant individually at a 0.05 level might be significant in a multivariate model.

14. TABLES, LISTINGS AND FIGURES

Planned tables, listings and figures (TLFs) intended to capture interim and final analyses described in the SAP will be reviewed by the Sponsor before going into production. TLF shells are maintained separately from the approved version of the SAP.

14.1. Programs and Quality Control

Report production and review will be conducted in accordance with FHI 360 BIOS Work Instructions (WI) 03003 (Verification of Analyses and Reports) and 03006 (Preparation and Review of Statistical Reports). In brief, a primary statistician-programmer for a given output will carefully review the program and output, verifying that no error message is highlighted in the “LOG” file and that titles, footers, footnotes, text body, etc. are correct. A second statistician-programmer will independently validate the output by checking the results against separately created SAS programs and checking textual material. Prior to delivery of any statistical output to Sponsor, the lead statistician will review the statistical package for internal inconsistencies or any items where clarifying notes will be helpful to the reviewer. Any package of final TLFs will also be thoroughly reviewed by the Director of Biostatistics and Data Sciences or designee before it is distributed.

14.2. Programming Conventions and Formatting

Reporting conventions will adhere, when possible, to the International Conference on Harmonization Guidance document E3, “Structure and Content of Clinical Study Reports”.

All TLFs will be in landscape format unless otherwise specified. All listings will include patient ID, treatment arm, randomization strata, age, race, and sex unless otherwise approved by the study team.

Each TLF will have at least two titles: the TLF number and description, and identification of the study population.

Footnotes will include the following information:

- Date of data extraction or lock (once applicable)
- Run date
- Study number and/or name
- Report name
- Name of program used to create the file
- Listing number for associated listing (for tables and figures)

